9.1 Exposure and Treatment Compliance

Exposure and treatment compliance will be summarized for all enrolled subjects by prior TPO-RA and overall.

Duration of exposure (in days) will be calculated as (Last dose date – First dose Date +1).

Number of tablets taken will be calculated as (total number of tablets dispensed – total number of tablets returned).

Number of tablets expected to take will be calculated as sum of (regimen end date – regimen start date +1)*prescribed treatment regimen of each regimen period.

Treatment compliance will be calculated as (number of tablets taken/number of tablets expected to take)*100. The treatment compliance will be summarized descriptively and also presented categorically (e.g. number and percentage of subjects with <80%, 80-100%, and >100-110%).

Data listings will provide details of subject exposure including treatment regimen, regimen start and end dates, regimen adjustments, number of tablets dispensed

Confidential

and returned according to the Drug Accountability eCRF page, and compliance as assessed by the Drug Regimen Adjustments eCRF page.

Duration of exposure, number of tablets taken, number of tablets expected to take, and treatment compliance of each subject will be listed as well.

9.2 Adverse Events

Adverse events (AEs) will be coded using MedDRA version 26.1 or later. The coding may be updated according to newly released versions of the dictionary.

Severity of AEs is categorized according to the following categories as entered in the eCRF: Mild, Moderate, Severe.

For investigator determined relationship to study drug, AEs are classified as "Related" or "Not Related".

AEs leading to discontinuation of avatrombopag are AEs where action taken is designated as "Drug Withdrawn" in the eCRF.

Two categories for Adverse Events of Special Interest (AESI) will be summarized and are defined based on terms in Standardized MedDRA Queries (SMQs) from MedDRA v26.1 or later:

1. Thromboembolic events - Any thrombotic or embolic event, whether arterial or venous – SMQ = Embolic and thrombotic events
2. Bleeding Events - Any clinically significant blood loss [e.g., bleeding events with CTCAE grade 3+ (based on AE severity [AESEV]>=3] – SMQ = Haemorrhage terms (excl laboratory terms)

[figure not shown]
TEAEs are defined as AEs occurring on or after the first dose of study treatment. TEAE will be tabulated by System Organ Class (SOC) and Preferred Term (PT) by prior TPO-RA (romiplostim and eltrombopag) and overall. TEAESI will be tabulated by AESI category and PT. Subjects with more than one TEAE in a SOC or PT will only be counted once per SOC or PT.

An overview summary table will include the number and percentage of all enrolled subjects with at least one:

- TEAE
- Serious TEAE
- TEAE of special interest (thromboembolic events and bleeding events)
- TEAE related to avatrombopag
- Severe TEAEs
- TEAE leading to study drug discontinuation

Summary tables of TEAEs will be provided for:

- TEAE (by SOC and PT)
- Serious TEAE (by SOC and PT)
- TEAE of special interest (by AESI category and PT)
- TEAE related to avatrombopag (by SOC and PT)

- Severe TEAEs (by SOC and PT)
- TEAE leading to study drug discontinuation (by SOC and PT)

Summary tables will also include number of events for each AE by SOC and by PT.

Listings of all adverse events reported after the consent form is signed (both TEAE and non-TEAE) will be provided and will include information such as the patient identifier, SOC, PT, reported term, date of onset/stop, duration of the event, TEAE, seriousness, severity, action taken, outcome, causality and relationship. A flag will be included in the listings to designate whether an adverse event is treatment-emergent.

Listings of adverse events will be provided for the following categories:

- All Adverse Events
- Serious AEs
- AEs of special interest (thromboembolic events and bleeding events)
- AEs related to avatrombopag
- Severe AEs
- AE leading to study drug discontinuation

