9.5 Adverse Events of Special Interest

The Investigator will monitor each subject for clinical and laboratory evidence for pre-defined AESIs throughout their participation in this study. The purpose for specifying these AESI is to enable further characterization of the clinical course and management of these events. An AESI may or may not be the consequence of treatment with avatrombopag.

The AESIs defined in this protocol include:

- Thromboembolic events (any thrombotic or embolic event, whether arterial or venous)
- Bleeding events (any clinically significant blood loss [e.g., WHO Grade 2 or higher]).

These events will be recorded on the AE eCRF page. The Investigator will assess and record any additional information on the AESI in detail on a SAE form (whether or not the event meets seriousness criteria in Section 9.2), to be submitted within 24 hours of awareness of the event. During the course of the study, additional AESIs may be identified by the Sponsor.

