APPENDIX B: WHO Bleeding Scale

Grade 0	No bleeding
Grade 1	Petechial bleeding
Grade 2	Mild blood loss (clinically significant)
Grade 3	Gross blood loss
Grade 4	Debilitating blood loss

a: Fogarty, 2012; Miller, 1981

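### SAP 9.2 illustrates the bleeding AESI with a CTCAE grade that neither document provides for, where Protocol 9.5 uses WHO Grade 2 or higher

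*SAP*

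**What the plan says.** - **Protocol 9.5** names two AESIs. One is thromboembolic events; the other is "Bleeding events (any clinically significant blood loss [e.g., WHO Grade 2 or higher". In Appendix B, WHO Grade 2 reads "Mild blood loss (clinically significant"), and Grade 1 is petechial bleeding.
- **Recording.** Protocol 9.5 says of AESIs: "These events will be recorded on the AE eCRF page". It adds: "The Investigator will assess and record any additional information on the AESI in detail on a SAE form", due within 24 hours whether or not the event is serious.
- **Protocol 10.2.1** commits to summarising AESIs by type, thromboembolic and bleeding.
- **Severity scale.** Protocol 9.1.2 has the investigator rate each AE on three levels. SAP 9.2 agrees: "Severity of AEs is categorized according to the following categories as entered in the eCRF: Mild, Moderate, Severe".
- **SAP 9.2 definition.** The two AESI categories "are defined based on terms in Standardized MedDRA Queries (SMQs) from MedDRA v26.1 or later". For bleeding, the text is "Any clinically significant blood loss [e.g., bleeding events with CTCAE grade 3+ (based on AE severity [AESEV]>=3", paired with the Haemorrhage SMQ without laboratory terms.
- **SAP 9.2 outputs.** AESIs appear in a row of the TEAE overview, in a table by category and preferred term, and in a listing.

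**The concern.** The SAP keeps the protocol's core idea of clinically significant blood loss but replaces its example. The new example names a grading system that appears nowhere else in either document. It attaches a numeric cut to a variable that the same SAP section describes as three words. The SAP neither says that it is departing from Protocol 9.5 nor gives a reason.

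Safety is the primary objective, and bleeding is one of only two pre-defined AESIs. If the SAP rule is not the protocol's rule, the AESI outputs carry the protocol's label but need not contain the events that sites were told to report under it. Two competent programmers could also produce different counts from the same data.

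**Working it through.** There is no stated figure to reproduce. The check sets the passages side by side and asks what each possible program would select.

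**Step 1. Compare the definitions.**

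| | Protocol 9.5 | SAP 9.2 |
|---|---|---|
| Core | clinically significant blood loss | the same |
| Example | WHO Grade 2 or higher | CTCAE grade 3+, through AESEV>=3 |
| Is the example's scale recorded? | Yes, at visits (Protocol 8.3, SAP 9.3.2) | No CTCAE grade; AE severity has three levels |
| Term set | none | Haemorrhage SMQ |

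**Step 2. Can the SAP cut be run?** It can only if Mild, Moderate and Severe are stored as 1, 2 and 3. The eCRF is not among the documents, so this coding is an assumption. Under it, the cut selects Severe. Neither document maps Severe to a CTCAE grade.

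**Step 3. Apply the cut.** The bleeding AESI becomes Haemorrhage SMQ events rated Severe, which is a subset of the Severe TEAE tables that the SAP already plans. Protocol 9.1.2.1 shows what this leaves out. Severe includes events that materially change clinical status or may need intensive treatment, so some clinically significant bleeds would be rated Severe. Moderate covers events that usually respond to specific treatment and carry no significant or permanent risk of harm. A treated WHO Grade 2 bleed can fit that description. Appendix B calls Grade 2 both mild and clinically significant, so this is the kind of event that the cut can remove.

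**Step 4. Ignore the cut as a mere example.** Every event coded to the Haemorrhage SMQ counts. Nothing then tests clinical significance, because SAP 9.2 names no field for it other than AESEV. Grade 1 bleeding enters wherever its preferred term belongs to the SMQ; the documents do not list the SMQ's terms.

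**Step 5. Can the effect be sized?** No. WHO grade is recorded by visit, from the subject's verbal answer. Severity is recorded by AE. The documents do not link the two and give no joint distribution. Protocol Table 1 reports contusion in 26%, epistaxis in 19%, gingival bleeding in 13% and petechiae in 11% of 128 avatrombopag-treated subjects. These figures show that bleeding-type AEs are common in this population. But Table 1 gives no severity or WHO grade, and median exposure in those studies was 7 months rather than 90 days, so no count for this trial follows.

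**Step 6. Where does the effect stop?** Three outputs depend on the definition: the AESI overview row, the AESI table by preferred term, and the AESI listing. The following do not:
- the all-TEAE, serious and Severe tables, and the all-AE listing (SAP 9.2);
- WHO grade by visit and at its highest over the study (SAP 9.3.2);
- rescue medication for bleeding (SAP 7);
- transfusions with bleeding as the reason (SAP 9.3.1).

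**The case against.** The strongest reply is that nothing of substance changed. Both documents define the AESI by clinically significant blood loss, and both thresholds follow *e.g.* If the SAP's example may be read loosely, so may the protocol's, and departure from a fixed protocol rule is then not proven. This stands in part: what is shown is that the examples conflict and that the SAP rule is ambiguous. But AESEV>=3 is a programming condition, not a clinical illustration, and it contradicts the severity scale in its own section.

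A second reply is that the WHO example cannot be programmed directly either, because no WHO grade is attached to each AE, so the SAP needed some AE-level rule. That is fair. It justifies stating an operational rule, but not one on a scale that is not collected.

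A third reply is that the eCRF and the mock tables, which the SAP keeps in a separate document, may settle the coding. They might, but they would not align the SAP text with Protocol 9.5.

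A fourth reply is that WHO Grade 2 or higher bleeding can be read from the SAP 9.3.2 tables. This stands, and it limits the harm. Those tables are planned as visit-level and overall grades only. They are not described as giving preferred term, seriousness or causality, so they do not replace the AESI summary.

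A reader might also cross the four bleeding grades with the three severities and count how many of the 12 combinations each rule selects. The documents do not support this as a measure of impact: the two scales sit at different levels, the combinations carry no weights, and some, such as debilitating blood loss rated Mild, may never occur.

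**Conclusion.** The SAP and protocol are inconsistent on this definition, and the text should be corrected before the SAP is final. SAP 9.2 rests its bleeding AESI example on a grade that is not collected. If the cut is applied, clinically significant bleeds rated Mild or Moderate leave the AESI outputs, assuming 1/2/3 coding. If it is ignored, no significance threshold remains.

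A reader might infer that the SAP undercounts bleeding or conceals it. The documents do not support that. The direction depends on which reading is programmed, the number of subjects affected cannot be computed, and bleeding is reported in several other places. Nor is the primary endpoint touched: it is the occurrence of AEs and SAEs. Site reporting within 24 hours follows the protocol, which the SAP does not alter. No test or decision rule uses the AESI count.

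**What to change.** In SAP 9.2:

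1. Delete the CTCAE and AESEV>=3 criterion.
2. Define the bleeding AESI as in Protocol 9.5. Count AEs that the investigator reported as bleeding AESIs, taken from the AE eCRF page and the AESI reports on the SAE form, and name the data field used.
3. Neither document shows that such a field, or the SAE-form data, reaches the analysis database. If it does not, count Haemorrhage SMQ events linked by date to a WHO assessment of Grade 2 or higher, and state this as an operational definition. For Day 15 onward, each assessment covers the time since the previous visit, so two bleeds in one interval would share a grade; the SAP should say how that is handled.
4. Keep the SMQ and the WHO grade as cross-checks: list subjects with Grade 2 or higher after baseline but no bleeding AESI, and Haemorrhage SMQ events not reported as AESIs.
5. Show Severe bleeding only as a subset row, with the AESEV coding stated.
6. Apply treatment emergence to the summary tables only. The SAP says "Listings of all adverse events reported after the consent form is signed (both TEAE and non-TEAE) will be provided", and AESIs are collected from consent (Protocol Appendix A, footnote j).

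The cost is SAP wording, one derivation and some record matching. Protocol 11.1.1 already calls for reconciliation with the safety database but does not spell out matching of non-serious AESI forms, so that part is added work. No visit or assessment is added. The bleeding AESI count may rise or fall relative to the SAP as programmed.

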7.2 Screening Visit (Visit 1)

The Screening Visit/Visit 1 must be completed within 28 days of the Baseline Visit/Visit 2, however, this visit may also be combined with the Baseline Visit/Visit 2.

The following procedures should be performed at the Screening Visit/Visit 1.

- Collect signed and dated informed consent prior to any other study procedures.
- Review of inclusion/exclusion criteria (Section 5) to confirm study eligibility.
- Record subject demographic information including race/ethnicity, date of birth and gender.
- Record ITP history that is available in the subject's medical record, including:
 - o Date of ITP diagnosis.
 - o Number of platelet transfusions in the previous 1 year, including date of last platelet transfusion.
 - Number of previous hospitalizations for ITP.
 - \circ Number of previous significant bleeding events (e.g., blood loss $\geq 1/2$ cup).
 - Most recent dose level and duration of previous treatments with eltrombopag and/or romiplostim, including qualifying eltrombopag/romiplostim treatment over the 90 days prior to study entry.
 - Other previous treatments for ITP, including duration.
 - O History of splenectomy (yes/no).
 - History of thromboembolic events.
- Record the reason for switching to avatrombopag from eltrombopag or romiplostim.

- Record subject-reported responses to brief questions (to be provided) regarding the prior administration of eltrombopag or romiplostim.
- Record any data on Additional Safety Information (Section 9.1.1) or (AESIs) (Section 9.5) that have occurred since the subject signed the ICF.
- Record any AEs that have occurred since the subject signed the ICF.
- Record any concomitant medication use, including concomitant ITP medications.
- Instruct subject on when to return for the Baseline Visit/Visit 2 if the Screening Visit/Visit 1 will not be combined with the Baseline Visit/Visit 2.

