9.1 Adverse Events

An AE is defined as any untoward medical occurrence in a subject administered a pharmaceutical product, which does not necessarily have a causal relationship with this treatment. An AE can therefore be any unfavorable and/or unintended sign (including an abnormal laboratory finding), symptom, or disease temporally associated with the use of an investigational medicinal product. All AEs, including observed or volunteered problems, complaints, or symptoms, are to be recorded on the appropriate eCRF.

AEs will be monitored and documented from the time of informed consent until study participation is complete. Subjects should be instructed to report any AE that they experience to the Investigator. Beginning with the informed consent signature, Investigators should make an assessment for AEs at each visit and record the event on the appropriate AE eCRF. Events associated with disease progression should not be reported as AEs or SAEs. However, if in the Investigator's opinion the disease progression is manifesting in an unusual or uncharacteristic manner, the associated events should be reported as AEs/SAEs, as appropriate.

Wherever possible, a specific disease or syndrome (i.e., diagnosis) rather than individual associated signs and symptoms should be identified by the Investigator and recorded on the eCRF. However, if an observed or reported sign or symptom is not considered a component of a specific disease or syndrome by the Investigator, it should be recorded as a separate AE on the eCRF. Additionally, the condition that led to a medical or surgical procedure (e.g., surgery, endoscopy, tooth extraction, or transfusion) should be recorded as an AE, not the procedure.

Any medical condition already present at Screening should not be reported as an AE unless the medical condition or signs or symptoms present at Screening change in severity, frequency or seriousness at any time during the study. In this case, it should be reported as an AE.

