4.3.5 Partial Dates

For the purpose of inclusion of appropriate data records in the analysis, some partially missing dates will have date imputation performed. However, these imputations will be limited to table summaries; listings will retain the date as entered in the database. The following imputations will be performed:

Medications:

- If a start date is missing the day
 - Set to the 1st of the month
- If a start date is missing the day and month
 - Set to January 1st if study treatment began the year prior to the year of medication start
 - Set to January 1st if the medication is known to start in a year prior to study treatment
 - If the medication and the study treatment start the same year, the medication start date will be set to the study treatment start date.
- No medication end dates will be imputed
- No completely missing dates will be imputed. If, after imputation, it cannot be determined whether a medication was taken prior or concomitantly, it will be considered a concomitant medication.

Adverse Events:

- If a start date is missing the day
 - Set to the 1st of the month, or the same day as treatment start if it is the same month and year as treatment start
- If a start date is missing the day and month
 - Set to treatment start date if it is the same year as treatment start; otherwise set to January 1st if it is the year after treatment start.
- No adverse event end dates will be imputed
- No completely missing start dates will be imputed. If, after imputation, it cannot be determined if an adverse event is treatment-emergent, it will be considered treatment-emergent for analysis purposes.

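### The TEAE definition has no worsening clause, so an AE that starts between consent and first dose and worsens on avatrombopag may be left out of every AE summary table, depending on the subject's consent date

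*SAP*

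**What the plan says.** SAP 9.2 gives the definition: "TEAEs are defined as AEs occurring on or after the first dose of study treatment". SAP 4.3.5 shows that the AE start date decides the matter. Its rule for a start date without a day is: "Set to the 1st of the month, or the same day as treatment start if it is the same month and year as treatment start". Its default is: "If, after imputation, it cannot be determined if an adverse event is treatment-emergent, it will be considered treatment-emergent for analysis purposes".

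Collection begins earlier. Protocol 9.1 says: "AEs will be monitored and documented from the time of informed consent until study participation is complete". On timing, Protocol 7.2 says: "The Screening Visit/Visit 1 must be completed within 28 days of the Baseline Visit/Visit 2, however, this visit may also be combined".

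Worsening is addressed only in Protocol 9.1: "Any medical condition already present at Screening should not be reported as an AE unless the medical condition or signs or symptoms present at Screening", and then "change in severity, frequency or seriousness at any time during the study". The same section limits worsening of laboratory and examination findings to those present at Screening in a similar way.

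The primary endpoint (Protocol 3.1, SAP 3.2.1) is the occurrence of AEs and SAEs. In SAP 9.2 the overview table and the six summary tables (all, serious, special interest, related, severe, leading to discontinuation) are restricted to TEAEs. Other AEs appear only in listings, with a flag for treatment-emergence.

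**The concern.** A pre-dose complaint that becomes severe or serious, or leads to withdrawal of avatrombopag, is information the primary objective is meant to capture. Under a rule based only on onset, the pre-dose start date fixes its status whatever happens on drug. The protocol's worsening rule does not help, because an event that began after Screening was not present at Screening. No rule in either document covers it.

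The second issue is consistency. The length of the consent-to-dose window is set by scheduling. Two subjects with the same clinical course relative to first dose can be counted differently because one consented earlier. That is an unwanted property in a single-arm study whose safety results are descriptive counts.

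**Working it through.** No stated figure in the plan depends on this definition, so the check applies the documents' rules to constructed cases.

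**Rules used**
- First dose is Day 1 and there is no Day 0 (SAP 4.3.2).
- Onset before consent: a condition present at Screening, reportable when it changes (Protocol 9.1). AE date = day of worsening.
- Onset on or after consent: an AE in its own right (Protocol 9.1). AE date = day of onset, assuming one record that keeps that date.
- TEAE if AE date ≥ Day 1 (SAP 9.2).
- Worsening is placed on Day 20 in every case. Consent is on Day -28 or Day -14 (split visits) or on Day 1 (combined visit).

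| Onset | Consent Day -28 | Consent Day -14 | Consent Day 1 (combined) |
|---|---|---|---|
| Day -35 | TEAE | TEAE | TEAE |
| Day -20 | not TEAE | TEAE | TEAE |
| Day -10 | not TEAE | not TEAE | TEAE |
| Day -1 | not TEAE | not TEAE | TEAE |
| Day 5 | TEAE | TEAE | TEAE |

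For onset on Day -10 and consent on Day -14, the AE date is Day -10, which is before Day 1, so the event is in no AE summary table. With consent on Day 1 the same complaint was present at Screening. Its change on Day 20 is the reportable event, and 20 ≥ 1 makes it a TEAE. For onset on Day -20 the answer changes between consent on Day -28 and on Day -14, so even two split-visit subjects can differ. If worsening on or after Day 1 also counted, all 15 cells would be TEAEs.

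**Size.** Two figures are needed that the documents do not give: q, the share of split-visit subjects with an AE that starts in the window and worsens on drug, and s, the share of subjects with split visits. Per 100 enrolled, subjects with such an omitted event = 100 × q × s. All values of q and s below are assumptions:
- q = 1%, s = 25%: 100 × 0.01 × 0.25 = 0.25
- q = 2%, s = 50%: 100 × 0.02 × 0.50 = 1
- q = 5%, s = 50%: 100 × 0.05 × 0.50 = 2.5
- q = 10%, s = 100%: 100 × 0.10 × 1 = 10

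The results are by prior TPO-RA, with about 50 subjects in each group, so one omitted subject is 1/50 = 2% of a column.

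**The case against.** The strongest objection is that the outcome depends on a source not provided. If the eCRF completion rules open a new AE record when severity changes, that record has a post-dose start date and is already a TEAE under SAP 9.2. This stands as a condition on the conclusion. Neither document requires such a record, so the count rests on an unstated convention.

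Screening might also mean the whole screening period, which SAP 4.1.1 runs to the day before Baseline. That would narrow the gap, but it sits awkwardly with AE collection from consent, and neither document adopts it in the worsening rule.

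The events are not hidden. They are flagged in the listings, and worsening bleeding would still be tabulated by WHO grade (SAP 9.3.2). This also stands, although that is not an AE table and non-bleeding events have no equivalent. A subject with another TEAE would still count in the overview row for at least one TEAE.

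A reader might infer more than the text supports:
- **A difference between sites.** SAP 5.2 records combined visits by subject, and nothing makes combining a site policy.
- **A risk raised by stopping the prior TPO-RA in the window.** No washout is required and only same-day dosing is excluded (Protocol 4.1), so prior treatment may continue until just before Day 1.
- **A known net downward bias.** The partial-date rules in SAP 4.3.5 push some events the other way, into the TEAE set.

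**Conclusion.** The gap is real on the text. SAP 9.2 has no worsening clause, and the protocol's rule does not reach an AE that starts after Screening and before first dose. If such an AE keeps one record with its original onset date, its worsening on avatrombopag is absent from all AE summary tables for the primary endpoint, and whether the same course counts depends on the subject's consent date.

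The conclusion rests on three assumptions: a single AE record, Screening read as Visit 1, and a start date known to fall before dosing. The size cannot be derived from the documents and is probably small. The 0.25 to 10 subjects per 100 shown above is an assumed range, not an estimate, and it does not support a claim that serious or severe events in particular will be lost. The point merits correction because it touches the primary endpoint and the correction is short.

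**What to change.** In SAP 9.2, define a TEAE as an AE with onset on or after first dose, or an AE with earlier onset that worsens in severity, frequency or seriousness on or after first dose. The three criteria match those in Protocol 9.1.

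State one recording convention: either a new record dated at the worsening, or a flag on the original record. Do not use both. SAP 9.2 also tabulates numbers of events, so counting the original AE and a second record would count one course twice. Say explicitly that each course contributes once to the event totals.

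Leave the Protocol 9.1 wording on conditions present at Screening as it is. Moving its cut-off to first dose would stop the reporting of AEs that start between consent and dosing and do not change, which conflicts with collection from consent.

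The cost is a short SAP addition and a check that the date of worsening can be obtained from the AE record. The AE items named in SAP 9.2 include onset and stop dates, but no date of change in severity, so the eCRF completion rules may need a line. TEAE counts may rise slightly.
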